6A. In lay language, briefly summarize the objective and significance of the research. COVID-19 has impacted the health and social fabric of individuals and families living across the United States; and it has disproportionately affected people living in urban communities with co-morbidities, those working in high-risk settings, refusing or unable to adhere to CDC guidelines, and more. Social determinants of health (SDH), such as stigma, racial discrimination, xenophobia, incarceration, and poverty have been associated with increased exposure to COVID-19 and increased deaths. Marginalized communities, defined as low-income and racial/ethnic minority neighborhoods, where residents experience increased barriers (e.g., inadequate housing, high-risk jobs) to prevention and treatment, bear disproportionately higher rates of co-morbidities associated with more severe cases of COVID-19. While effective and potent vaccines are becoming more available, it will take time to reach herd immunity and it is unclear how long newly-developed vaccines provide protection and how effective they are against emerging variants. Therefore, prevention methods recommended by the Centers for Disease Control and Prevention (CDC) – i.e., testing, hand-washing, social distancing, contact tracing, vaccination, and quarantine -- are essential to reduce the rates of COVID-19 in marginalized

communities. Research about COVID-19 testing and vaccine uptake in these communities must occur in real time and it must account for the fast-changing landscape of the pandemic, including the impact of vaccine availability on testing uptake. Two cost-effective, evidence-based, and culturally appropriate interventions have been effective in engaging people in HIV prevention and treatment – these can be adapted and tested to help address COVID-19 prevention needs. Specifically, Navigation Services (NS) have been shown to increase HIV testing and adherence to treatment while addressing structural barriers that deter treatment engagement in high-risk communities; and Brief Counseling (BC) has been shown to increase HIV treatment engagement.

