[name] has an ongoing grant (3 R01 MD010629-04S2 – From here after referred to as COVID-19 NJ Study)) which aims to optimize an adaptive intervention to increase testing, and access to treatment and to prevention of COVID-19 infections in a medically or socially vulnerable sample of 670 people in Essex County, NJ. The COVID-19 NJ Study is under the North Jersey Community Research Initiative (NJCRI) IRB oversight, entitled *Optimization of a new adaptive intervention to increase COVID-19 testing among people at high risk in an urban community*, Protocol #: CWCVIDSUPP-UIUC-NJCRI 102497-18274-267805 and has a reliance agreement in place with UIUC.

The new project, COVID-19 IL Study, which is being reviewed by the UIUC IRB, proposes to expand the NJ project to include a sample of 548 people in Illinois. We will use the same protocol that was used in NJ in addition to de-identified data that is currently being collected by the COVID-19 NJ Study. The final study sample will include 670 people from NJ and 548 people from IL for a total of 1,218. Data from the 670 people in NJ will be treated as secondary data and data from the 548 people in IL will be treated as primary data under the COVID-19 IL Study IRB protocol.

The COVID-19 IL Study will use Multiphase Optimization Strategy (MOST) and Community-Based Participatory Research (CBPR) principles and best practices to help facilitate recruitment and to make results readily available to the population. Illinois participants will be randomized two separate times: First, into two distinct groups to receive: (1) navigation services or (2) informational brochure. We aim to help participants to get a COVID-19 test between baseline and the first follow-up (7 days post baseline). Second, after completing the first follow-up, participants are then randomized again to continue with the original intervention or switch to a new one. We then collect data at 2; 5; 12; and 24 weeks post-baseline follow-ups.

The COVID-19 IL Study specific aims include:

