Primary Aims: (1) To examine the effectiveness of an adaptive intervention to increase COVID-19 testing and adherence to CDC-recommendations of preventive behaviors – social distancing, hand-washing, mask-wearing, vaccination- on comparable but distinct samples. We will control for baseline, time, demographics and COVID risk; (2) To examine the immediate and medium-term impact of the adaptive intervention on COVID testing and adherence to recommendations by collecting follow up data at 2,5,12, and 24 weeks post baseline.

Implementation aim: To collect intervention implementation data (context, cost, barriers, lessons learned) and develop implementation materials (facilitator training, intervention manual, treatment fidelity measure).

6B. Indicate if your research includes any of the following:

- Secondary data (use of data collected for purposes other than the current research project) De-identified collected data by the COVID-19 NJ Study, described in final paragraph of 6A and COVID-19 testing results collected from CBHC.
- Data collected internationally (include [International Research Form](#))
- Translated documents (include [Certificate of Translation Form](#) and translated documents)
- Research activities will take place at Carle (include documentation (email or letter) from Carle stating that the review of your [Research Services Request Form](#) is complete)

6C. Letters of support from outside institutions or entities that are allowing recruitment, research, or record access at their site(s) are attached. Yes Not Applicable

Letters of support from NJCRI and CBHC are in the NIH proposal (p.129- 132 of the attached proposal PDF)

Section 7. PROCEDURES

7A. Select all research methods and/or data sources that apply.

- Surveys or questionnaires, *select all that apply:* Paper Telephone Online
- Interviews
- Focus groups ("Critical Dialogue" Sessions)
- Field work or ethnography
- Standardized written, oral, or visual tests
- Taste or smell testing
- Intervention or experimental manipulation
- Exercise and muscular strength testing
- Noninvasive procedures to collect biological specimens (e.g., hair and nail clippings, saliva, etc.)
- Noninvasive procedures to collect physiological data (e.g., physical sensors, electrocardiography, etc.)
- Procedures involving radiation
- Recording audio and/or video and/or taking photographs
- Recording other imaging

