All participants will be asked to complete follow ups 4 and 5. We will collect screening data via phone, and in-person baseline assessment, and follow- ups at 2, 5, 12 and 24 weeks follow-ups. Participants will be encouraged to complete the surveys online, using their phones, a tablet, or computer. They can also request to meet the outreach workers at CBHC or a public place to complete the data collection using a study tablet, as long as they agree to adhere to the most current public health recommendations (e.g., social distancing).

After each assessment, participants will be asked to provide extensive locator information, on forms used for the parent study, including formal and informal contacts who can reach the participant in a variety of contingencies. During the follow-up period, outreach workers will maintain monthly contact with participants by mail or phone and will update locator information. Randomization and data collection will be done online using Redcap. We will voice record all Critical Dialogue sessions with participants' consent and will randomly select 20% of them for analysis.

The research team will randomly select 35 participants at each site who decline to be tested for COVID-19 and invite each of them to complete an in-depth, one-on-one, qualitative interview lasting about 30 minutes. After providing written informed consent, participants will be assigned code names and asked to talk about their experiences with the intervention, barriers they faced to testing and adhering to public health guidelines, and their ideas about how to address these barriers. The interviews will be digitally voice-recorded, transcribed and entered into Atlas.ti for storage and analysis. Transcripts and Atlas.ti files will be identified only by code name.

Additionally, data from the COVID-19 NJ Study will be analyzed. These data include the exact same surveys as the data being collected in Illinois. The data is being collected under NJCRI's IRB number. UIUC deferred to the NJCRI IRB because all the NJ data is being collected there. The NJ data will be de-identified and shared electronically by the NJ research assistant using Box. The NJ data will then be merged with the Illinois data for analysis.

The figure below illustrates the study design:

COVID-19 Testing

Section 8. PERFORMANCE SITES TO INCLUDE INTERNATIONAL, SCHOOL, AND COLLABORATIVE STUDIES

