COVID-19 Treatment Cascade Optimization Study

NCT05305443

Statistical Analysis Plan

3/30/2022

Statistical Analysis Plan

Data analysis: Aim 1. We will estimate the (1) differences in the effects of first-stage interventions (NS vs brochure), (2) differences in the effects of second-stage interventions (BC vs NS among those who complete testing and referral vs CD among testing decliners), and (3) differences in the effects of selected adaptive interventions on acceptance of testing and adherence to IL recommendations. For differences between NS and brochure, cross-tabulations of the interventions with each outcome will be generated, and crude odds ratios comparing the two will be calculated. For the effects of second-stage and third-stage interventions, we will perform a similar analysis as that for the first-stage interventions but on corresponding subsets as indicated in the specific comparison groups. The estimation of effects of embedded adaptive interventions will use weighted and replicated estimation techniques. Under these procedures, the data set will be restructured wherein an individual's outcome will be replicated in the data set depending on the number of adaptive interventions consistent with this outcome. Since randomization at both stages is based on equal probabilities, weighing is not necessary. The restructuring of the data set as described allows the utilization of standard statistical software for parameter estimation and hypothesis testing. A generalized linear model using logistic regression will be performed where estimation of model parameters will be done using generalized estimating equations due to the presence of replicated subjects. We will then use tests of contrasts to compare selected adaptive interventions. The analysis of the adaptive interventions will be done using PROC GENMOD in SAS. To adjust for baseline characteristics and test for their moderating effects, we will incorporate these terms and their interactions with first-stage, second-stage, and adaptive interventions in their respective models. Only the baseline characteristics will be used for adjustment, as outcomes of the first-stage intervention are biased if incorporated into this model. Odds ratios, 95% CI, and Wald's test for the effect of interventions and covariates will be obtained from these results. Sex/gender and race/ ethnicity will be among these covariates that we will consider for adjustment and moderation analysis.

Interim analyses

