An interim analysis will be conducted bi-monthly by study analysts once data collection starts. This will include the development of syntax to clean the data (e.g., missingness analysis, identification of data entry errors, recoding variables). The key variables will be reviewed. Descriptive data will be presented to PIs and members of the NCCB. The NCCB will review preliminary findings presented by the PIs on a bi-monthly basis to address any potential adverse reactions that may occur and any safety concerns that may arise. If any participants are found to be unresponsive to the intervention, or getting worse during the course of the study, an NCCB sub-committee will discuss the case and the participant may be terminated from the study and referred to relevant services in the community. The PIs will meet weekly with the study staff to review the study protocol adherence and address any potential problems. The PIs will also have weekly supervision meetings with intervention facilitators to review the results from fidelity ratings and address any potential deviance from interventions.

Methods for additional analyses (e.g., subgroup analyses)

Aim 2: To identify other predictors of these outcomes, we will include these variables as covariates using logistic regression analysis. We will model probabilities of testing behavior (completed vs testing decliners) and adherence to IL recommendations as functions of the first-stage intervention and other covariates in the logistic regression analysis.

Qualitative component analysis: Critical dialog sessions and in-depth interviews will be digitally audio-recorded and transcribed. Data will be entered into Atlas ti, a qualitative data processing program. Analysis rooted in phenomenology and grounded theory will include continuous coding, comparison, and recoding to yield categories and connect experiences and themes. The analysis will focus on participant reports about their experiences with the intervention, barriers to testing and adherence to IL recommendations, and suggestions on how to address these barriers.

Methods in analysis to handle protocol non-adherence and any statistical methods to handle missing data

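### Aim 1 concerns two distinct samples that will be merged, but the plan commits to no site term, site-specific estimate or site-by-intervention test

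*Protocol*

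**What the plan says.** - **Aim.** Protocol 6A, Primary Aims, sets out to examine the adaptive intervention "on comparable but distinct samples. We will control for baseline, time, demographics and COVID risk". Site is not in that control list.
- **Samples.** Protocol 6A: "The final study sample will include 670 people from NJ and 548 people from IL for a total of 1,218". New Jersey is secondary data from a separate ongoing study, while "data from the 548 people in IL will be treated as primary data".
- **Handling.** Protocol 7F: "The NJ data will then be merged with the Illinois data for analysis".
- **First-stage analysis.** SAP, Data analysis, Aim 1, for navigation services (NS) against brochure: "cross-tabulations of the interventions with each outcome will be generated, and crude odds ratios comparing the two will be calculated". Later-stage comparisons follow the same approach on subsets. The embedded adaptive interventions are compared with a GEE logistic model.
- **Covariates.** The SAP would enter baseline characteristics and their interactions with the interventions. It adds: "Sex/gender and race/ ethnicity will be among these covariates that we will consider for adjustment and moderation analysis". The Aim 2 model is written "as functions of the first-stage intervention and other covariates in the logistic regression analysis".

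The SAP does not mention New Jersey, the merge or the total of 1,218, and it does not say which data set any analysis uses.

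**The concern.** The aim speaks of two samples, and the protocol keeps them apart in status (primary and secondary), oversight and location. No specified analysis is committed to telling them apart. An analyst could follow the SAP to the letter and produce only pooled results.

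New Jersey supplies 55% of the merged data. If the effect were confined to New Jersey, a pooled estimate could still be clearly positive and be reported as effectiveness in both samples, including Illinois, the sample this protocol enrols. The opposite pattern could be hidden in the same way. Because site is neither required nor excluded, the decision to examine it would be made after data are available, so either a reassuring or a discordant site result would be post hoc.

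**Working it through.** **Inputs from the documents.** New Jersey 670 and Illinois 548 (Protocol 6A). The sum is 670 + 548 = 1,218, which reproduces the stated total. Shares are 670/1,218 = 55.0% and 548/1,218 = 45.0%. Randomisation is with equal probabilities (SAP, Aim 1). I take this to apply at both sites because the protocol says they share a protocol. That gives 335 per arm in New Jersey, 274 in Illinois and 609 pooled.

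**Assumed inputs.** The documents give no testing rates, effect sizes or power. I assume brochure testing rates of 20% to 50%, a range of New Jersey effects, no Illinois effect, and a two-sided 5% level (suggested by the planned 95% CIs).

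**1. Illustration: 40% under brochure at both sites, odds ratio 2.0 in New Jersey, 1.0 in Illinois.**
- New Jersey NS odds = 2.0 × 0.40/0.60 = 1.333, so the rate is 1.333/2.333 = 57.1%. Illinois NS rate = 40%.
- Pooled NS rate = (335 × 0.571 + 274 × 0.40)/609 = 49.4%. Pooled brochure rate = 40.0%.
- Pooled odds ratio = (0.494/0.506)/(0.40/0.60) = 1.47.
- SE of log OR = √[1/(609 × 0.494) + 1/(609 × 0.506) + 1/(609 × 0.40) + 1/(609 × 0.60)] = 0.116.
- 95% CI = exp(0.383 ± 1.96 × 0.116) = 1.17 to 1.84; z = 3.30, p ≈ 0.001.
- The Illinois estimate alone would be 1.00, with SE = √[2/(274 × 0.40) + 2/(274 × 0.60)] = 0.174 and 95% CI 0.71 to 1.41.

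The same steps with a New Jersey odds ratio of 1.8 give a pooled 1.38 (p ≈ 0.005). With 1.5 they give 1.25 (p ≈ 0.052).

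**2. Chance of a significant pooled result with no Illinois effect.** The pooled difference is 0.55 × the New Jersey difference. Over brochure rates of 20% to 50%:

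| New Jersey effect | Pooled test significant | Interaction test significant |
|---|---|---|
| 10 points | 49–63% | 41–49% |
| 15 points | 83–92% | 74–79% |
| 20 points | 97–99% | 93–95% |

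The interaction test is a Wald test on the difference between the two sites' log odds ratios.

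**3. Is a site main effect enough?** No. In 3,000 simulated trials per setting, with a 15-point effect in New Jersey only, the share favouring NS significantly was:

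| Brochure rate | Crude pooled | Pooled with site main effect | Illinois alone |
|---|---|---|---|
| 30% | 86% | 86% | 3% |
| 40% | 83% | 84% | 3% |

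Only site-specific estimates and an interaction test expose the pattern.

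**4. What Illinois alone can show.** With 274 per arm, 80% power needs a difference of about 10 to 12 points, against about 7 to 8 points pooled, over the same brochure rates.

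**The case against.** **Pooling is a described choice.** Illinois expands the New Jersey project under the same protocol and surveys, as one trial of 1,218, and a pooled average effect is a legitimate target. The aim's wording does not expressly demand a separate claim for each state. This stands as a defence of having a pooled estimate. It does not show that effects are equal, or explain how the pooled estimate addresses distinct samples.

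**The SAP permits site.** Enrolment site is a baseline characteristic, the named covariates are only examples, and interactions are planned. So it would be too strong to say that the plan excludes site. What stands is that nothing commits to it.

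**The illustration assumes its conclusion.** Any pooled trial can be positive with one null subgroup. The figures show what is possible and do not predict this trial.

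**Stronger readings that the documents do not support.**
- *Every SAP analysis is stated to use the merged file.* The protocol's merge sentence makes that the likelier reading, but the SAP is silent and refers to adherence to IL recommendations.
- *New Jersey uses a different testing provider.* The Illinois provider is named; the documents do not say who tests in New Jersey.
- *Site cannot be separated from calendar period.* New Jersey data were still being collected when the protocol was written and no dates are given, so the periods may overlap. The remark in 6A that research of this kind "it must account for the fast-changing landscape of the pandemic, including the impact of vaccine availability on testing uptake" is general motivation, not an analysis commitment.
- *New Jersey interim results are already known to the investigators.* Nothing says so.
- *The crude odds ratio is biased when site is omitted.* With equal-probability randomisation at each site, omission does not materially confound the first-stage contrast. If the odds ratio is 2.0 at both sites and brochure rates are 20% and 60%, the crude value is 1.77. That is non-collapsibility, a marginal against a conditional odds ratio. With 30% and 40% it is 1.98.

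**Conclusion.** The point holds as a gap in prespecification. Aim 1 refers to distinct samples and the data are merged, yet the plan guarantees no analysis that distinguishes them or says which data set it uses. A significant pooled result is compatible with no effect in Illinois. Under the assumed rates this would happen in about half to nearly all trials as a New Jersey-only effect rises from 10 to 20 points. Those probabilities rest wholly on assumed testing rates, an effect confined to New Jersey and 1:1 allocation at both sites. The absence of any commitment to site rests on the text alone. The matter should be corrected in the SAP; it is not a flaw in the randomised comparison itself.

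**What to change.** Amend the SAP as follows.

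1. State that the analyses use the merged New Jersey and Illinois data, and identify any that do not.
2. Replace crude pooled odds ratios with site-stratified or site-adjusted ones.
3. For NS against brochure and the selected adaptive-intervention contrasts, prespecify the Illinois estimate and the New Jersey estimate, each with a 95% CI, and a site-by-intervention test, all beside the pooled estimate.
4. Rest any claim about both samples on the site-specific estimates, and do not read a non-significant interaction as consistency.
5. For second-stage subsets, use site adjustment only, since splitting them by site would leave thin cells.
6. Note that a site difference may also reflect place, local delivery or calendar time.

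The cost is SAP wording and a few extra model runs on a variable that the merged file should already hold. Site-specific intervals will be wider, and the interaction test has limited power: about 41% to 49% for a 10-point difference under the assumed rates.

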Brochure: This intervention includes two different electronic brochures: One with information about COVID-19 testing (including where and how to get tested), and one with information about COVID-19 prevention and treatment. The brochures will be updated in real time to reflect the most recent CDC public health recommendations. Brochures will be e-mailed to all participants automatically by Redcap upon randomization and one week after they complete the baseline.

Once randomized, all participants will receive the brochure that includes information about testing at CBHC. Navigators will speak to their clients about testing, and, if the participant is interested, they can schedule the COVID-19 test for participants. Note participants will not be pressured to test. They will simply receive the information on how to do so and we will ask them to do it prior to completing their follow-up, if they choose to get tested. Home tests will not be accepted for the purposes of the study.

One week post-baseline, participants will complete the first follow-up survey. Those who received a COVID-19 test between baseline and Follow-up 1 will be randomized to either continue to receive their original intervention (NS or Brochure) or to switch to receive Brief Counseling. Those who fail to get a COVID-19 test between baseline and first follow-up will be randomized to continue the original intervention (NS or Brochure) or switch to receive Critical Dialogue:

Brief Counseling (BC): Brief Counseling is a 15-minute post-COVID-19 test session delivered by a trained licensed clinician in person or via Zoom Conferencing. In the session, the clinician shares the test results and offers recommendations and information about COVID-19 treatment and prevention. Clinicians will be members of the research team and employed by CBHC.

Critical Dialogue (CD): Critical Dialogue includes one two-hour “focus group” session facilitated in person or online by a trained licensed facilitator. Group critical dialogue is prompted by thematic images developed by the Newark Community Collaborative Board (NCCB) to foster a deeper understanding of how systematic stigma, feelings of rage as victims of discrimination, and/or apathy may impact participants’ beliefs and behaviors related to COVID-19 and empower participants to make critical choices to protect their health and the health of their communities.

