COVID-19 test procedures and HIPPA protected data collection and sharing: Enrolled participants interested in getting tested for COVID-19 will either come into CBHC or meet the trained outreach worker to collect the sample. CBHC holds a Clinical Laboratory Improvement Amendment (CLIA) Certificate of Waiver and uses the Lumira Dx SARS-CoV-2 Ag Test (see attached instruction manual). The outreach worker will be using N-95 mask and gloves. Participants are asked to collect their own nasal sample and hand it over to the outreach worker who processes it. It takes 15 minutes to obtain the test results and participants are informed immediately. They receive the study brochure that provides

information about how to prevent COVID-19 and what to do if tested positive. As soon as the results come out, the outreach worker logs into Redcap and records the test completion date and results.

In cases where the sample is collected outside of CBHC, the participant will be asked to collect the sample following the instructions, place it into a plastic bag, and hand it to the outreach worker. The collection bag will have the participants' study code number written on it and it is transported in a cooler container back to CBHC. Once the sample is processed, the outreach worker calls the participant to provide the test results and logs the information in Redcap. They receive the brochure when they turn in the sample.

With participants' permission, we will share the COVID-19 test results and some identifying information (e.g., zip codes) with the Duke Clinical Research Institute (DCRI). HIPPA data will be downloaded from Redcap automatically including only data that was authorized by participants to be shared with the CDCC. This will be a CVS file which is downloaded into Box Health. The file is then uploaded weekly into the Duke data portal (see attached CDCC Data guidance pdf).

Participants who report not getting tested in follow-up 3 will be invited to participate in a Critical Dialogue session before completing Follow-up 4.

[figure not shown]

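### The first-stage testing window closes when the Follow-up 1 survey is completed, not on a fixed day, so late surveys lengthen it, and lateness that differed by arm would bias NS versus Brochure

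*Protocol*

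**What the plan says.** **Target time.** Protocol section 7F: "One week post-baseline, participants will complete the first follow-up survey". Section 6A also puts the first follow-up at 7 days.

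**Tested status.** Section 7F: "Those who received a COVID-19 test between baseline and Follow-up 1 will be randomized" to stay on their intervention or switch to Brief Counseling (BC). The mirror rule begins "Those who fail to get a COVID-19 test between baseline and first follow-up will be randomized" and leads to staying or switching to Critical Dialogue (CD).

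**Trigger for the second randomization.** Section 6A: "after completing the first follow-up, participants are then randomized again".

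**Instruction to participants.** Section 7F adds that nobody will be pressured to test, and then: "we will ask them to do it prior to completing their follow-up, if they choose to get tested".

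**Test date.** Section 7F (test procedures) has the outreach worker enter the completion date and result in REDCap. For samples taken away from the clinic, "Once the sample is processed, the outreach worker calls the participant to provide the test results and logs the information in Redcap".

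**Analysis.** The SAP (Data analysis, Aim 1) names the outcome as acceptance of testing and compares NS with Brochure by cross-tabulation and crude odds ratios. It gives no time window for the outcome.

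**Schedule.** Later in section 7F the assessments are "follow- ups at 2, 5, 12 and 24 weeks follow-ups", with no week 1. Section 7E gives four follow-ups, while section 7F also refers to follow-ups 4 and 5.

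**The concern.** A binary outcome compared by a crude odds ratio needs the same observation time in both arms. Here the period in which a test counts ends at an event that the participant controls. A person who completes the survey on day 10 has three more days to become a tester than a person who completes it on day 7.

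The arms differ in staff contact. NS participants meet a navigator, may receive follow-up calls at a frequency agreed with the navigator, and can have a test scheduled for them. The Brochure intervention is e-mailed. That contact could delay the survey (a test is already booked) or bring it forward (more prompting). Either way, the NS versus Brochure odds ratio would mix the effect of the intervention with a difference in window length.

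The same open window decides who enters the BC or the CD stratum, so it also affects who is in the second-stage comparisons and the embedded adaptive interventions.

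**Working it through.** **1. When the window closes.** Section 7F counts tests up to Follow-up 1. Section 6A re-randomizes after Follow-up 1 is completed. The request to test is tied to completing the survey. Together these make survey completion the closing event.

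**2. Whether anything caps it.** One week is a target. Neither document gives a visit window, a grace period or a latest date. Late surveys are foreseen, since section 7F collects alternative contacts for finding people whose survey is due. A participant who never completes Follow-up 1 has no defined closing date.

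**3. Whether the analysis absorbs it.** The SAP's intention-to-treat grouping and multiple imputation deal with non-adherence and missing values. Neither equalizes observation time. The recorded test date would allow a fixed-day endpoint, but no passage uses it for that.

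**4. Size.** The plan states no testing rate or effect size for this comparison, so there is no figure to reproduce. Assume a constant daily testing chance *h*, identical in both arms, so that the true effect is null. Then P(*k*) = 1 − (1 − *h*)^*k*, and OR = [P(10)/(1 − P(10))] ÷ [P(7)/(1 − P(7))]. The 10-day and 7-day windows are assumptions, applied to whole arms.

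| *h* | Tested by day 7 | Tested by day 10 | Spurious OR |
|---|---|---|---|
| 2% | 13.2% | 18.3% | 1.47 |
| 4% | 24.9% | 33.5% | 1.52 |
| 6% | 35.2% | 46.1% | 1.58 |

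For 4%: (0.335/0.665) ÷ (0.249/0.751) = 1.52. If the arms are swapped, the odds ratio is 1/1.52 = 0.66.

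**5. A one-day difference (8 versus 7 days).** Write P(*t*) = 1 − (1 − p7)^(*t*/7), with an assumed 7-day rate p7 of 10% to 50%. The spurious OR runs from 1.15 (11.3% v 10.0%) to 1.21 (54.7% v 50.0%).

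The rejection rate of a two-sided 5% test (inferred from the SAP's 95% CI) is Φ((d − 1.96·SE0)/SE1) + Φ((−d − 1.96·SE0)/SE1). Here d is the difference between the two proportions a and b, p̄ is their mean, n is the number per arm, SE0 = √(2p̄(1 − p̄)/n) and SE1 = √([a(1 − a) + b(1 − b)]/n). With equal allocation and complete data:

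- Illinois alone, n = 548/2 = 274: 8% to 20%.
- Pooled, n = 1,218/2 = 609: 12% to 38%.

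**6. Equal lateness.** With both arms at day 10 and *h* = 4%, both show 33.5% and the OR is 1.00. The null comparison is unbiased, but the quantity is 10-day testing (33.5%) rather than 7-day testing (24.9%).

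**7. With a fixed cut-off by test date.** Both arms are counted over the same days. The same null gives OR 1.00 and 5% rejection, whatever day the survey arrives.

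**The case against.** The strongest reply is that the protocol does set a time. With Follow-up 1 due at one week, the request to test before the survey can be read simply as a request to test within the week. That is fair. The gap is a missing visit window and counting rule, not a missing target.

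It can also be said that the tested/not-tested sentences in section 7F are a routing rule for the second randomization, and that the SAP never defines its outcome as testing before Follow-up 1. This also stands, but it leaves the SAP outcome with no window at all. Section 6A describes the first-stage aim over the same interval, so the survey-based rule is the only one an analyst could take from the text.

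Three stronger readings are tempting, and the documents do not support them:

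- *Participants are told to hold the survey until they have tested.* No passage invites late submission, and the protocol says that participants will not be pressured to test. If some did hold the survey, but equally in both arms, the null odds ratio would stay at 1.
- *Navigator contact lengthens the NS window.* The calls are described as being about services received and still needed, not about survey timing. NS participants are also urged to test promptly. Locator contacts and outreach workers' monthly contact are not limited to NS. No timing data are given.
- *Off-site samples handed over before the survey are classed as untested.* The protocol says that results are logged after processing. It does not say that the processing date is entered as the test date, and the routing rule asks whether a test was received, not when it was logged.

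The odds ratios above shift a whole arm. They do not model selective holding of surveys and are not a forecast.

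**Conclusion.** The concern holds as a design weakness with a cheap remedy. As written, the first-stage testing window ends at survey completion and has no stated limit, and the planned comparison does not account for observation time. Bias requires lateness to differ between NS and Brochure. That is possible but not shown, and it could go either way.

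The size is conditional. If one arm's window were three days longer, a true null would appear as an odds ratio of about 1.5, under a constant and equal daily testing chance of 2% to 6%. A one-day difference would give about 1.15 to 1.21, for 7-day rates of 10% to 50%. If lateness is the same in both arms, the cost is a change in what is estimated and in who is routed as tested, not a false effect.

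This should be changed. It does not show that the trial's result is biased.

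**What to change.** 1. **Reconcile the schedule first.** The one-week Follow-up 1 (sections 6A and 7F) has to be squared with the 2, 5, 12 and 24 week schedule and the count of four follow-ups (sections 7E and 7F). The documents do not settle which governs, so the cut-off day is for the study team to set.
2. **SAP endpoint.** Define first-stage testing as a study-accepted test dated within that fixed number of days of baseline, from the date in REDCap, whenever the survey is submitted. For off-site samples, use the collection date.
3. **Protocol wording.** Replace the request to test before completing the survey with one tied to the chosen day. Send Follow-up 1 on its due day regardless of testing. State a visit window and a rule for late or missing surveys.
4. **Reporting.** Report time from baseline to Follow-up 1 by arm.
5. **Routing.** Status at re-randomization can still send people to the BC or CD stratum.

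**Cost.** Wording in both documents and, if collection date is not already captured, one REDCap field. For pooled analyses, the team should confirm that the de-identified New Jersey data carry the test date or the days from baseline. The documents do not say. A few late testers will be first-stage failures yet be routed as tested, so endpoint and routing status should be kept as separate variables.
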